6.1. Summary of Study Design

Study A4 is a multicenter, randomized, double-blind, placebo-controlled, Phase 3 study comparing solanezumab with placebo for 240 weeks in approximately 1150 participants ages 65 to 85 years old with preclinical AD, defined as having evidence of brain amyloid pathology without clinically evident cognitive impairment at screening. Participants who met entry criteria were randomized in a 1:1 ratio (approximately 575 per treatment arm) to solanezumab or placebo once every 4 weeks. Participants were randomized within the site by education – high (13 or more years) or low (12 or less years) and the presence of one or more apolipoprotein E gene (APOE) ϵ 4 alleles (yes, no). The primary hypothesis being tested is that the cognitive decline at the end of the placebo-controlled period will be significantly less for solanezumab than for placebo. Participants completing the placebo-controlled period of the study can opt to participate in the open-label period of the study that will last for up to 204 weeks or until the primary analyses of the placebo-controlled period of the study are completed and reviewed.

At the beginning of the COVID-19 pandemic, a hiatus was implemented to allow participants to pause study activities without missing visits and resume when COVID safety mitigations were in place (for example, vaccines, home infusions, etc.). The hiatus extended the end of the placebo-controlled period for up to 9 months and the placebo-controlled period will be administratively closed in December 2022.

Figure A4.SAP.1 illustrates the study design.

Abbreviation: V = visit.

Figure A4.SAP.1. Illustration of study design for Clinical Protocol A4.

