6.2. Determination of Sample Size

In order to develop an appropriate measure of cognitive decline in a preclinical population, we tested several combinations of measures using data from longitudinal studies in clinically normal populations, including the ADNI; the AIBL; the ADCS-PI trial; and the HABS.

Sample size and power at 4.5 years (240 weeks) for the PACC were estimated using data from ADNI and HABS. Estimates were obtained by applying appropriate assumptions regarding treatment difference, SD, and attrition for a 4.5-year study in a preclinical AD population. In ADNI, the difference in the composite change between participants with and without elevated brain amyloid at 240 weeks was 2.13 (SD=2.85). Similarly, in HABS, the difference in the composite change between participants with and without elevated brain amyloid at 240 weeks was 2.66 (SD=3.08). Given the ADNI-derived estimate of SD at 240 weeks of SD=2.85 and 30% attrition, the total N=1150 provides 80% power (5% 2-sided alpha) to detect a treatment difference of 0.532 points or $0.532/2.13 = 24.9\%$ of the amyloid group difference. Similarly, based on the HABS estimate of SD at 240 weeks of SD=3.08, the study has 80% power to detect a treatment difference of 0.570 points or $0.570/2.66 = 21.4\%$ of the amyloid group difference.

For the open-label period, the estimated mean PACC difference between cognitively normal participants with and without elevated brain amyloid at 336 weeks is 2.95 (SD=3.77) based on ADNI and 4.74 (SD=3.99) based on HABS. Accounting for the administrative censoring that will be induced by the common close design of the open-label period, and assuming an overall attrition rate of 30%, about 266 PACCs are expected to be available at 336 weeks. The visit-to-visit correlation is estimated to be about 0.5. Under these pilot estimates, 266 PACCs at 336 weeks would provide 80% power to detect a randomized group (early-start vs delayed-start treatment with solanezumab) difference of about 0.9 PACC points. This change of 0.9 PACC points reflects 30% of the difference between amyloid-positive and -negative participants based on ADNI, and 20% of that difference based on HABS.

Sample size for the study was determined assuming an MMRM analysis prior to the interruption caused by the COVID-19 pandemic. Applying the NCS approach in simulated trials with a COVID-19 pandemic interruption suggests the study has 94% power to detect an effect size of 0.75 PACC points at 240 weeks.

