7.1. General Considerations

Unless otherwise noted, all tests of treatment effects will be conducted at a 2-sided alpha level of 0.05; 2-sided confidence intervals will be displayed with a 95% confidence level. All tests of interactions between treatment and other factors will be conducted at an alpha level of 0.05.

All analyses will follow the modified intent-to-treat (mITT) principle unless otherwise specified. An ITT analysis is an analysis of data by groups to which the participants are assigned by random allocation, even if the participant does not take the assigned treatment, does not receive the correct treatment, or otherwise does not follow the protocol. An mITT analysis is an ITT analysis for all participants who have a baseline and at least 1 postbaseline measure. All safety analyses will be done using the safety population. Analysis populations are described below (Section 7.5).

When change from baseline is assessed, participants will be included in the analysis only if both a baseline and a post-baseline measure are available. Unless otherwise defined, a baseline measure is the last non-missing observation collected prior to the first infusion of study medication. End point is the last non-missing post-baseline measurement.

For MMRM analyses, observations collected at non-scheduled visits (see Section 7.2) will not be included in the analyses. For NCS and MMRM analyses, unless otherwise specified, an unstructured covariance structure will be used. If the unstructured covariance structure matrix results in a lack of convergence, the following covariance structures will be used in sequence: heterogeneous Toeplitz covariance structure, heterogeneous autoregressive covariance structure, heterogeneous compound symmetry covariance structure and homogeneous compound symmetry covariance structure.

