7.12.4.1. Placebo-Controlled Period

Analysis of the change from baseline to endpoint of each vMRI parameter will be done. The analysis will be done using an analysis of covariance (ANCOVA) model with fixed effects of baseline vMRI value, treatment, age at baseline, education, APOE4 Carrier Status (yes/no), and baseline florbetapir cortical SUV_r. The null hypothesis is that the difference in least square mean between the solanezumab group versus placebo equals zero.

Additionally, due to the disassociation of visit and time caused by the COVID disruption, an analysis treating time as a continuous variable will be conducted. Each vMRI parameter will be regressed on time, treatment, APOE4 Carrier Status (yes/no), and age at baseline, with the constraint that the two treatment groups have the same y-intercept. Slopes between the two treatment groups will be compared.

To assess the relationship of vMRI parameters and efficacy outcomes with treatment, Spearman's rank correlation coefficient will be obtained on change from baseline to endpoint for each vMRI parameter with change from baseline to endpoint for PACC, ADL-Prevention Questionnaire, CFI, CDR-SB and C3. These correlations will be obtained separately within each treatment group and all participants.

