7.12.5.1. Placebo-Controlled Period

Analysis of the change from baseline to endpoint for each CSF parameter will be done. The dependent variable for each CSF parameter is its change from baseline to endpoint. The analysis of the change from baseline will use an analysis of covariance (ANCOVA) model with fixed effects of (i) baseline CSF, (ii) treatment, (iii) APOE4 Carrier Status (yes/no), and (iv) age at baseline. The null hypothesis is that the difference in least square mean between the solanezumab group versus placebo equals zero.

Additionally, due to the disassociation of visit and time caused by the COVID disruption, an analysis treating time as a continuous variable will be conducted. Each CSF parameter will be regressed on time, treatment, APOE4 Carrier Status (yes/no), and age at baseline, with the constraint that the two treatment groups have the same y-intercept. Slopes between the two treatment groups will be compared.

To assess the relationship of CSF parameters and efficacy outcomes with treatment, Spearman's rank correlation coefficient will be obtained on change from baseline to endpoint for each CSF parameter with change from baseline to endpoint for PACC, ADL-Prevention Questionnaire, CFI, CDR-SB and C3. These correlations will be obtained separately within each treatment group and all participants.

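### The vMRI–cognition correlations use change to the last available value without accounting for follow-up time, which builds a modest spurious association into them, strongest for vMRI with PACC

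*SAP*

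**What the plan says.** SAP 7.1 (General Considerations): "End point is the last non-missing post-baseline measurement". No week is attached.

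SAP 7.12.4.1 (vMRI, placebo-controlled period) has three parts.
- A treatment comparison: "Analysis of the change from baseline to endpoint of each vMRI parameter will be done", by ANCOVA.
- A second treatment comparison with time as a continuous variable, a common intercept and a contrast of slopes. It was added because COVID-19 separated visit from time.
- The correlations: Spearman's "rank correlation coefficient will be obtained on change from baseline to endpoint for each vMRI parameter with change from baseline to endpoint for PACC", and likewise for the ADL Prevention Questionnaire, CFI, CDR-SB and C3. "These correlations will be obtained separately within each treatment group and all participants". No time adjustment, common week, hypothesis or significance level is given.

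The florbetapir, flortaucipir, plasma and CSF sections describe their correlations in the same way.

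Follow-up will be unequal. SAP 6.2 plans for 30% attrition. SAP 6.1 describes a hiatus extending the placebo-controlled period by up to 9 months. Protocol Attachment 1 schedules MRI at Weeks 12, 84, 168 and 240 and at early termination, and PACC every 24 weeks. A footnote allows early-termination procedures to be omitted. SAP 7.2 keeps off-schedule data from early discontinuers for analyses other than MMRM.

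**The concern.** Brain volume and PACC are both expected to worsen with time on study. Someone whose last scan and last PACC fall in year 1 tends to show little change on either; someone followed to Week 240 or beyond tends to show more on both. Ranking everyone together turns length of follow-up into a common cause of both variables. A non-zero coefficient then appears even when, at any given duration, one change says nothing about the other.

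These coefficients are the SAP's stated means of assessing how the imaging measures relate to clinical outcome. Part of any reported brain–cognition link would reflect when people left rather than biology. The SAP recognises the time problem in the preceding paragraph, but corrects it only for the treatment comparison.

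**Working it through.** **Plan's own figure.** The SAP gives none for these correlations. The nearby 80% power statement for PACC supplies only the attrition rate and a scale for drift; whether it reproduces does not bear on this point.

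**Inputs**
- Attrition 30%; about 575 per arm, 1150 in total (SAP 6.1, 6.2).
- PACC drift a, in SDs over 240 weeks: 2.13/2.85 = 0.747 (SAP 6.2, ADNI). This is an amyloid-group difference standing in for absolute drift, which the documents do not give. A lower value of 0.35 is assumed.
- vMRI drift b: not in the documents; assumed 0.25 to 2 SD.
- Dropout timing: not in the documents; assumed uniform over 240 weeks.

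**Closed form.** Let T be time of last assessment/240, with 70% at 1 and 30% uniform on (0,1).
- Mean T = 0.7 + 0.3 × 0.5 = 0.85
- E[T²] = 0.7 + 0.3/3 = 0.80
- Var(T) = 0.80 − 0.85² = 0.0775

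With PACC change = aT + error and vMRI change = bT + error, the errors independent with SD 1:

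r = ab·Var(T) / √[(1 + a²Var(T))(1 + b²Var(T))], and Spearman ≈ (6/π)·arcsin(r/2).

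- a = 0.747, b = 1: 0.0579/√(1.0432 × 1.0775) = 0.055; Spearman 0.052 (simulated 0.051).
- a = 0.35, b = 0.25: 0.0068/√(1.0095 × 1.0048) = 0.007; Spearman 0.006.
- a = 0.747, b = 2: 0.1158/√(1.0432 × 1.3100) = 0.099; Spearman 0.095 (simulated 0.089).

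Letting half the variance come from random slopes, and adding a 0–39 week extension in half of completers, raises the simulated maximum to 0.121.

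**If tested at two-sided 0.05 (an assumption).** For Spearman 0.052 and n = 575: 0.052 × √572 = 1.24, and P(Z > 1.96 − 1.24) ≈ 24%; simulation gave 24%. The table gives simulated rates with a = 0.747 and 1,500 replicates per cell, over three follow-up patterns (early-termination assessment, scheduled visits only, hiatus extension) and two variance models.

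| vMRI drift | n = 575 | n = 1150 |
|---|---|---|
| 0.25 SD | 6–8% | 7–11% |
| 0.5 SD | 10–15% | 14–24% |
| 1 SD | 22–38% | 41–68% |
| 1.5 SD | 42–67% | 68–93% |
| 2 SD | 58–82% | 85–98% |

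Rates are much lower elsewhere:
- PACC drift 0.2 SD with vMRI 0.5 SD: 4.5–5.4%.
- n = 100: 5–7%.
- 10% dropout at n = 1150: 5.5–16%.
- No drift in one measure: 4.7%.

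**Do the remedies work?**
- Equal follow-up: 5.1%.
- Only pairs with both values at Week 240 or later, 575 randomized: 3.7–6.5%. This survives the hiatus because little time variation remains. With e = 39/240 = 0.1625, Var(T) among completers = 0.5e²/3 − (0.5e/2)² = 0.00275, about 1/28 of 0.0775.
- Partial Spearman on follow-up time: 4–8.5% without the hiatus, but up to 16.5% with it and strong drift.

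**vMRI ANCOVA.** If the treatment effect is linear in time, the last-observation effect is mean(T) times the Week 240 effect. With early-termination scans, 1 − 0.85 = 15% smaller. With scheduled scans only (dropouts before Week 12 contribute nothing): (0.7 + 0.09 × 0.05 + 0.105 × 0.35 + 0.09 × 0.70)/0.985 = 0.816, so 18% smaller.

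**The case against.** **No test is planned.** The SAP says only that coefficients will be obtained. The 0.05 level in SAP 7.1 is attached to treatment effects ("all tests of treatment effects will be conducted at a 2-sided alpha level of 0.05") and to interactions. A reader might infer from the table that the plan carries a known, grossly inflated error rate. It does not: those rates require a test the SAP does not specify and drifts the documents do not give. This stands. What remains is bias in the coefficient.

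**The problem is not general to all biomarkers.** The shared wording (for example "change from baseline to endpoint for each CSF" parameter) invites that reading. But florbetapir PET and lumbar puncture are scheduled post-baseline only at Visit 66 and early termination, so most pairs sit near the end of treatment. Lumbar puncture is optional and offered in three countries. Plasma is assayed at Weeks 12 and 240, and nothing in the documents establishes a trend in it. Protocol 10.3 expects minimal CDR-SB change over 3 years. This also stands; the vMRI figures should not be carried across.

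**Endpoint may mean Visit 66.** Protocol 10.2.11.2 uses it that way for MRI, and the section covers only the placebo-controlled period, so a value from any later time is not meant. But the SAP's explicit definition is the last non-missing value, and that is what a programmer would follow.

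**Completers are reported separately.** Table A4.SAP.2 lists PACC and vMRI outputs for the Completers Population, where follow-up is closer to common. It does not say that the correlations are repeated there.

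**The vMRI treatment comparison.** A reader might also conclude that this is left diluted. The slope analysis in the same section already addresses unequal follow-up, so the only open question is which analysis leads.

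**Conclusion.** The point holds for the correlations, chiefly vMRI with PACC. As defined, they mix any participant-level relationship with length of follow-up. The spurious part is about 0.01–0.12, under vMRI drift of 0.25–2 SD, PACC drift of 0.35–0.75 SD, 30% uniform dropout and, at the upper end, the hiatus extension. That is modest, but at these sample sizes it could be mistaken for a finding. No single error rate can be attributed to the plan: if tested, it could be near 5% or above 90%.

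The effect is small for CDR-SB, small CSF subsets and any biomarker without a trend, and limited for florbetapir and CSF. The primary analysis is unaffected. The 15–18% attenuation of the vMRI ANCOVA depends on a linear effect and uniform dropout, and the slope analysis already covers it.

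**What to change.** 1. Compute the correlations on final-visit pairs: Visit 66 MRI with Visit 66 PACC. In Attachment 1 as it reads, CDR, CFI, the ADL questionnaire and C3 are last scheduled at Visit 63 (Week 228), so name that visit for those scales and confirm it against the schedule.
2. Because this drops non-completers and describes completers only, supplement it with a correlation of participant-level rates of change that uses all values and actual assessment times, for example the slope correlation from a bivariate mixed model (not simulated here). Do not rely on rank-based partial correlation alone, given the hiatus.
3. Reconcile SAP 7.1's definition of end point with the protocol's use of the word for Visit 66, and state which applies in each biomarker section.
4. State that the coefficients are descriptive, or name the test and level.
5. For the vMRI treatment comparison, at most state that the continuous-time slope analysis takes precedence over the last-observation ANCOVA.

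Cost: SAP wording and programming; no new data.

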7.12.4.2. Open-Label Period

Volumetric MRIs are not collected during the open-label study period.

7.12.5. Analyses of CSF Data

Analyses of CSF biomarkers will be done for the subset of participants who have a lumbar puncture.

The CSF parameters analyzed will include the following:

- total $A\beta_{1-40}$
- total $A\beta_{1-42}$
- free $A\beta_{1-40}$
- free $A\beta_{1-42}$
- total tau, and
- p-tau.

7.12.5.1. Placebo-Controlled Period

Analysis of the change from baseline to endpoint for each CSF parameter will be done. The dependent variable for each CSF parameter is its change from baseline to endpoint. The analysis of the change from baseline will use an analysis of covariance (ANCOVA) model with fixed effects of (i) baseline CSF, (ii) treatment, (iii) APOE4 Carrier Status (yes/no), and (iv) age at baseline. The null hypothesis is that the difference in least square mean between the solanezumab group versus placebo equals zero.

Additionally, due to the disassociation of visit and time caused by the COVID disruption, an analysis treating time as a continuous variable will be conducted. Each CSF parameter will be regressed on time, treatment, APOE4 Carrier Status (yes/no), and age at baseline, with the constraint that the two treatment groups have the same y-intercept. Slopes between the two treatment groups will be compared.

To assess the relationship of CSF parameters and efficacy outcomes with treatment, Spearman's rank correlation coefficient will be obtained on change from baseline to endpoint for each CSF parameter with change from baseline to endpoint for PACC, ADL-Prevention Questionnaire, CFI, CDR-SB and C3. These correlations will be obtained separately within each treatment group and all participants.

7.12.5.2. Open-Label Period

CSF biomarkers are not collected during the open-label study period.

7.13. Safety Analyses

Two different safety datasets will be created. The safety placebo-controlled (safety-PC) dataset consists of visits 1-66 and allows for comparisons between solanezumab-treated participants and placebo-treated participants; the safety open-label dataset consists of visits 66-117 during which all participants are treated with solanezumab. Participants will be analyzed according to the treatment group to which they were randomized. All safety measures will be summarized for each dataset in which they were collected.

Safety will be assessed by summarizing and analyzing AEs, laboratory analytes, vital signs, electrocardiograms (ECGs), magnetic resonance imaging (MRI), immunogenicity and additional safety data collected during the treatment period.

Safety analyses for the treatment period will include comparisons between solanezumab and placebo. All hypotheses will be tested at a 2-sided 0.05 significance level. No adjustments for multiple comparisons will be made.

7.13.1. Analyses of Adverse Events

Adverse events will be coded according to established Medical Dictionary for Regulatory Activities (MedDRA) terms and summarized by MedDRA System Organ Class and Preferred Term.

7.13.1.1. Analyses of TEAEs, SAEs, Discontinuation Due to AEs

Treatment-emergent adverse events (TEAEs) will be defined as events that first occurred or worsened after first infusion of study drug (generally Visit 6). Should there be insufficient data for AE start date or stop date to assess for treatment emergence, the adverse event will be considered treatment emergent.

An overview of AEs, including the number and percentage of participants who died, experienced serious adverse events (SAEs), discontinued due to adverse events and who experienced TEAEs, will be provided. Comparison between treatments will be performed using Fisher's exact test.

Summaries of AEs by decreasing frequency of preferred term within system organ class will be provided for the following:

- Preexisting conditions
- TEAEs
- TEAEs by maximum severity
- TEAEs occurring in greater than or equal to 5% of participants by preferred term
- SAEs ,and
- AEs reported as reason for discontinuation.

These summaries will include numbers and percentages of participants with TEAEs. Treatment comparisons will be carried out using Fisher's exact test.

For events that are gender-specific, the denominator and computation of the percentage will include only participants from the given gender.

7.13.1.2. Subgroup Analyses of TEAEs

Subgroup analyses of TEAEs will also be done. The subgroups will include age at baseline (≥ 65 and < 75 years, ≥ 75 and < 85 years), gender, and race (dichotomized based on distribution of race at baseline). For each subgroup variable, a Breslow-Day test of homogeneity of odds-ratios between treatment groups will be performed on the incidence of each TEAE.

7.13.1.3. Analyses of TEAEs by Dose

For participants treated with solanezumab, summaries of treatment-emergent adverse events will be displayed with events assigned to the dose (400 mg versus 1600 mg for participants assigned to solanezumab, with events occurring at the 800 mg level assigned to the 1600 mg group, and low dose placebo and high dose placebo for participants assigned to placebo based on the blinded dose level) that the participant was taking at the time of the event. At the first occurrence of a high dose for a participant, all subsequent observations will also be considered as high dose. Events will be reported as frequencies and rates, adjusted for the amount of time until the event for participants who experienced the event or total time on the specified dose for those who did not experience the event. Treatment-emergence will be defined separately for each dose level, with the time period immediately preceding the dose as the baseline period. An adverse event that first appears or worsens in severity subsequent to the dose will be considered treatment-emergent.

7.13.1.4. Analyses of Specific Clusters of TEAEs

In addition, the proportion of participants within the following specific clusters of TEAEs will be summarized and treatment comparisons will be conducted using Fisher's exact test:

- infusion-related reactions including anaphylaxis and urticaria, overall and broken out by immediate (same day as infusion) versus delayed
- suicidal ideation or behaviors
- hemorrhagic stroke
- cardiac ischaemic events
- cardiac arrhythmias, and
- amyloid-related imaging abnormality – hemorrhage (ARIA-H, also known as microhemorrhage).

The listing of preferred terms of the TEAEs corresponding to each specific cluster above is provided in [Appendix 2](#).

